Test Up Now Education Program

NCT04304001

Document Date: 1/26/2022

Study Protocol and Statistical Analysis

Study Protocol

The TUNE-UP study is designed as a two-group pretest/posttest pragmatic randomized controlled trial. The study uses the parallel group, two arm superiority trial design with 1:1 allocation ratio. The pragmatic trial aims to test the effectiveness of the intervention in the setting of community health centers. To conduct the intervention trial, 115 participants were randomized at the time of enrollment following completion of the baseline survey. The two experimental arms are: 1) an intervention group which receives the adapted Screen to Save (S2S) educational materials, a tailored brochure for African Americans on colorectal cancer (CRC) screening with input from focus group research, and CHA in-person and cellphone education and counseling supplemented by text messages; and 2) a control group which receives the brochure only. Participants in both study arms received communication from their CHC to receive their stool-based testing kit. The primary outcome is CRC screening by 12-months post-intervention (i.e., receipt of the stool-based test). The intermediary CRC screening outcome is measured at 3-months. Secondary outcomes included CRC knowledge and CRC screening self-efficacy.

Study participants and setting

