All statistical analyses were performed using SAS 9.4. First, summary statistics were generated for all variables. Then bivariate analyses were conducted for key variables to compare differences between the intervention and control arms. Proportions calculated from categorical variables were compared using a chi-square test; means obtained continuous variables were compared using two-sample t-test. The multivariate analyses were conducted using the GEE procedure in SAS that implements the generalized estimating equations regression. Analyses were performed using an intent-to-treat approach that includes all participants randomized. Significance tests were two-sided and employed an overall significance level of $\alpha=0.05$. For each arm, the proportion of participants who receive CRC screening by 12 months was computed. The chi-square test was used to compare the two treatment arms for screening receipt. If the proportion of participants receiving CRC screening in the intervention arm is at least 15% higher than that in the control arm, the intervention will be determined to be effective. In addition, since our sample size gets small when participants are stratified by community health center or sex, we will use Fisher's exact test to assess the effect of the intervention. To assess the influence of key covariates (age, income, marital status, education, insurance status) on the primary outcome, logistic regression analysis was employed. In addition, to investigate treatment effects over time (baseline, 3 months, and 12 months), we will estimate hazard ratios by fitting Cox proportional models using time-varying covariates. In these models, the receipt of CRC screening will be regressed at each actual time point on time elapsed since baseline to test for an interaction between time and treatment group. The basic model will be repeated, adjusting for age, income, marital status, education, and any other significant covariates at baseline. To test the proportional hazard assumption, the Kaplan-Meier curve and the Schoenfeld residuals will be used for fixed and time-varying covariates, respectively.

Mediation and moderation analyses will be conducted to determine why and when variables are related, respectively. We will focus on specific mediators to include CRC perceived susceptibility, CRC self-efficacy, and CRC knowledge in the conceptual model.

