The complexities of the relationships between the exogenous variables (X) and the endogenous variables (Y) as a function of the mediators will be examined using three separate regression models. We will ensure that the assumptions of continuous measurements (i.e., that all variables are measured on a continuous scale), normality (i.e., normal distribution of all variables), independence (i.e., that there is no correlation of errors from one observation to another observation), and linearity (i.e., evidence linear relationships among the variables) are met. We will assess direct causality and indirect causality using standardized regression coefficients (i.e., betas) to determine the direction and magnitude of the effect of one variable upon the other variable.

We will confirm that the mediators (i.e., CRC perceived susceptibility, CRC self-efficacy, and CRC knowledge) are caused by the exogenous variables X and are also the causes of the endogenous variables Y. We will also determine if X loses its significance when M is included in the model. Specifically, we will perform regression analyses and confirm the significance of the relationship between the exogenous (i.e., independent variable - IV) and endogenous variables (i.e., dependent variable - DV), the exogenous and mediator variable, the mediator and the endogenous variables in the presence of the IV, and lastly, we will confirm the lack of significance (or the meaningful reduction in effect) of the relationship between X and Y in the presence of the mediators.

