Additionally, we will assess the moderator variables (i.e., sex, health literacy, family history of cancer) to determine under what condition (i.e., when) a given predictor X/independent variable (IV) is related to an outcome Y/dependent variable (DV). We will assess whether the moderation effect is enhancing (i.e., that is, increasing the moderator would increase the effect of the predictor on the outcome), buffering (i.e., that is, increasing the moderator would decrease the effect of the predictor on the outcome), or antagonistic (i.e., where increasing the moderator would reverse the effect of the predictor on the outcome). We will apply hierarchical multiple regression to examine the effects of the moderating variable. We will assess the interaction effect between X and M and whether or not such an effect significantly predicts the occurrence of Y. All variables will be standardized to facilitate data interpretation and avoid multicollinearity. We will fit a regression model predicting the outcome from both the predictor and moderator variables. We will check that both the effect of the predictor and the effect of the moderator, as well as the model (R²) are statistically significant. Then, we will fit another regression model that includes the interaction effect of the first model and check for a statistically significant R² change and a statistically significant effect of the interaction term to determine if moderation is occurring (i.e., both are statistically significant).

Mediation analysis allows assessment of each covariate's impact on the primary outcome independent of whether the intervention's effect is significant; thus, adding to scientific understanding of the relevance of each. To examine the mediating effects on the primary outcome of each of the short items scored on a Likert-type scale, we will follow the strategy of Baron and Kenny. We will conclude that the candidate covariate is indeed a mediator of the effects of the intervention if: (1) the treatment group indicator is significant; and (2) the candidate covariate is significant, and the coefficient estimate of the treatment group indicator is smaller in absolute value than its counterpart in analysis.

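### The mediation plan names three constructs but adds an unreconciled rule that declares mediation for single Likert items, one at a time and without a treatment-to-mediator test

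*Combined protocol and SAP*

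**What the plan says.** All the relevant text is in the Statistical analysis section of the combined protocol and SAP, which describes mediation twice.

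- **Construct-level description.** The mediators are named: "We will focus on specific mediators to include CRC perceived susceptibility, CRC self-efficacy, and CRC knowledge in the conceptual model". The relations between exogenous variables, mediators and endogenous variables "will be examined using three separate regression models". The section then lists the steps to be confirmed: X to Y, X to mediator, mediator to Y given X, and loss or meaningful reduction of the X–Y relation once the mediators (plural) are in the model.
- **Item-level description.** After the moderation text, the section returns to mediation and applies the Baron and Kenny strategy to "each of the short items scored on a Likert-type scale". A candidate is declared a mediator if (1) the treatment indicator is significant, and (2) the candidate is significant and the treatment coefficient is smaller in absolute value than its counterpart. The rule is worded for one candidate covariate. It does not require that treatment change the candidate.

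The outcome is the trial's binary primary endpoint: "The primary outcome is CRC screening by 12-months post-intervention". The documents do not say how many items each construct has, how items are scored, how reliable they are, whether the mediators enter one model, how the two descriptions relate, or how the 0.05 level is handled across items.

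**The concern.** The two descriptions differ in unit (construct or item) and in criteria (with or without a treatment-to-mediator test). Only the item-level one is worded as a rule for concluding mediation. Two analysts could follow the same plan and name different mechanisms from the same data.

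Followed as written, the item rule has three weaknesses:

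- A single item measures its construct with error. This shrinks the estimated indirect effect and moves the remainder into the apparent direct effect.
- A candidate tested alone is credited with the effect of whatever it correlates with.
- Without a treatment-to-mediator test, an item that the intervention does not move can still be labelled a mediator.

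What is at stake is the explanatory result, that is, which construct is said to carry the intervention's effect.

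**Working it through.** The plan gives no power or error figure for mediation, so there is nothing to reproduce. The check is a simulation of the rule.

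**From the documents.** "115 participants were randomized at the time of enrollment following completion of the baseline survey"; 1:1 allocation; binary outcome; two-sided tests at 0.05.

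**Assumed, because the documents are silent.** Item reliability 0.3–0.5; five five-point items per construct; correlation r between the true mediator and a second construct of 0.3, 0.5 or 0.7. Treatment shifts each construct by 0.6 SD. The second construct has no effect on screening. Outcome model: logit P(screened) = −0.8 + 0.4·arm + 0.8·M, with M the true mediator. There were 3000 runs per setting, so the Monte Carlo standard error is at most √(0.25/3000) ≈ 0.9 points.

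**Step 1: expected attenuation.** The true indirect effect is 0.6 × 0.8 = 0.48 log-odds. With a mediator of reliability ρ, about ρ × 0.48 is recovered: 0.14 at 0.3, 0.24 at 0.5. The reliability of a k-item mean is kρ/(1+(k−1)ρ):

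- k=5: 1.5/2.2 = 0.68 and 2.5/3.0 = 0.83.
- k=6: 1.8/2.5 = 0.72 and 3.0/3.5 = 0.86.

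A separate six-item simulation (direct effect 0.3, intercept −0.95) recovered 0.14 and 0.24 with single items, and 0.35 and 0.42 with the six-item mean.

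**Step 2: part (2) of the item rule, and the joint model** (% of runs, five items)

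| r | Item reliability | True mediator: one item | True mediator: score | Non-causal: one item | Non-causal: at least one of five | Non-causal: score alone | Joint model: non-causal score significant | Joint model: true score significant |
|---|---|---|---|---|---|---|---|---|
| 0.3 | 0.3 | 40 | 80 | 7 | 27 | 13 | 6 | 83 |
| 0.3 | 0.5 | 65 | 86 | 11 | 31 | 15 | 5 | 90 |
| 0.5 | 0.3 | 40 | 79 | 14 | 44 | 30 | 8 | 76 |
| 0.5 | 0.5 | 64 | 86 | 20 | 51 | 35 | 7 | 83 |
| 0.7 | 0.3 | 42 | 81 | 21 | 61 | 52 | 12 | 64 |
| 0.7 | 0.5 | 63 | 86 | 38 | 73 | 59 | 8 | 69 |

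Adding six-item runs widens the ranges slightly:

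- One item of the true mediator: 40–66%. Its score: 78–87%.
- One non-causal item: 7–11%, 13–22% and 21–42% at r = 0.3, 0.5 and 0.7.
- At least one non-causal item: 27–32%, 44–54% and 61–77%.

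**Step 3: adding part (1).** Here treatment significance is taken from the model without the candidate; the rule does not say which model it means. The true mediator then passes in 21–37% of runs with one item and 44–50% with the score. One non-causal item passes in about 4–6%, 8–11% and 12–20% at r = 0.3, 0.5 and 0.7.

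**Step 4: treatment does not move the second construct** (reliability 0.4). One item still meets part (2) in about 5% (r=0.5) to 10% (r=0.7) of runs, and at least one of five in 22% to 35%. A treatment-to-mediator test is aimed at this error.

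**Step 5: scoring alone is not enough.** Tested one at a time at r=0.5, the non-causal score is labelled in 30–35% of runs, more often than a single item (14–20%). The joint model is what lowers this.

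**The case against.** The strongest reply is that the construct-level analysis is planned, complete with a treatment-to-mediator step, and that its last step may well mean a model holding all three mediators. That stands. A reader might infer that item testing replaces the constructs, or that the item rule governs the conclusion. The documents support neither reading, because they do not rank the two descriptions.

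The phrase about short items may also loosely mean short scales, and no instrument is described. That stands too, so a fix based on scores presumes instruments with several items. On that reading the noise problem shrinks, but one-at-a-time testing of correlated constructs remains.

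The size is open to challenge. If the second measure is error-free and only its own significance is counted, it is flagged in 18%, 44% and 71% of simulated trials at r = 0.3, 0.5 and 0.7, and in about 5% with both measures in the model. A reader might take these as the rule's error rate and the remedy's performance. They are neither: items are noisy, and the rule has further conditions. All magnitudes rest on assumed measurement properties.

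Finally, this is a secondary, explanatory analysis.

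**Conclusion.** The concern holds as an unreconciled pair of mediation descriptions, of which the item-level one is the weaker. Under the stated assumptions, relying on a single item lowers the chance that the true mediator meets part (2) from about 78–87% to 40–66%. A correlated construct with no effect on screening, if moved by treatment, has at least one item meeting part (2) in about 27–32%, 44–54% and 61–77% of trials at r = 0.3, 0.5 and 0.7. These are rates for part (2) alone; Steps 3 and 4 show how far single-item rates fall under the full rule, or when treatment leaves that construct unchanged. The direction follows from measurement error and correlation. The size depends on reliabilities, item counts and correlations that the documents do not give. The plan should be clarified before the mechanism is reported. Nothing here touches the primary comparison.

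**What to change.** Reconcile the two descriptions in the Statistical analysis section:

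1. State that the mediators are the scores for perceived susceptibility, self-efficacy and knowledge. Define the scoring, where an instrument has several items.
2. Fit one outcome model with arm and all three scores, and judge each mediator on its own path there.
3. Require the treatment-to-mediator path for each, as the construct-level description already does.
4. Report each indirect effect with a confidence interval.
5. Keep item-level results descriptive.

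The change is to wording and analysis code; nothing in the documents suggests that it needs new data. The cost is power when scores correlate. In the five-item runs, significance of the true mediator's score falls from 85–92% when fitted alone to 76–83% in the joint model at r=0.5, and from 86–91% to 64–69% at r=0.7. Six-item runs extend the joint-model upper ends to 85% and 71%. With imperfect reliability, false attribution drops to about 5–12% but does not disappear. In a run with 1150 participants (r=0.5, reliability 0.4) the non-causal score was still significant in about 30% of trials, so the report should describe mediator attribution as tentative.

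### The mediation rule requires a significant arm effect on screening, which defeats the plan's stated aim of learning from mediators whatever that effect shows

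*Combined protocol and SAP*

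**What the plan says.** All the relevant text is in the Statistical analysis section of the combined protocol and SAP.

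- The last mediation paragraph opens: "Mediation analysis allows assessment of each covariate's impact on the primary outcome independent of whether the intervention's effect is significant".
- Two sentences later, having adopted the Baron and Kenny strategy, it concludes that a covariate is "indeed a mediator of the effects of the intervention if: (1) the treatment group indicator is significant". A second condition asks for a significant covariate and a treatment coefficient that is smaller than its counterpart.
- The regression steps set out before this will "confirm the significance of the relationship between the exogenous (i.e., independent variable - IV) and endogenous variables". They end by planning to "confirm the lack of significance (or the meaningful reduction in effect) of the relationship between X and Y" once the mediators are in the model.

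The section plans standardized coefficients for direct and indirect causality. It plans no test or interval for an indirect effect that would allow a mediation conclusion without the total-effect condition.

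**The concern.** The analysis is introduced as useful whatever the arm comparison shows, but no mediator can be concluded unless that comparison is significant. Mediation is most needed when the primary result is null or borderline, because it can then show whether the intervention moved knowledge, self-efficacy or perceived susceptibility, and whether these predicted screening. The rule withholds the conclusion in that case.

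The gate is also a poor filter. In a trial of this size, the test of the total effect on a yes/no outcome can have much less power than the tests of the two paths that make up mediation. A real mediator can then be well supported on both paths and still fail because of the arm comparison.

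The rule does not name the model in which the treatment indicator must be significant. The mention of a counterpart coefficient points to the model without the mediator, and that reading is used here.

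**Working it through.** **Inputs from the document**
- Sample size: "115 participants were randomized at the time of enrollment following completion of the baseline survey", with 1:1 allocation. Taken as 58 intervention and 57 control.
- Two-sided tests at 0.05, with a chi-square test for screening receipt.
- The only effect size is the effectiveness threshold, "the intervention arm is at least 15% higher than that in the control arm". It is read here as 15 percentage points; the document does not say absolute or relative.

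**Assumptions.** The document gives no control screening rate, planned power or mediator effect size, so there is no stated figure to reproduce. Control rates and path strengths below are assumed. The chi-square stands in for the test of the treatment indicator.

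**Step 1: chance of passing the gate.** Worked example at 30% v 45%, by normal approximation:
- Pooled rate = (58×0.45 + 57×0.30)/115 = 0.376.
- Null standard error = √[0.376×0.624×(1/58 + 1/57)] = 0.0903. The observed difference must exceed 1.96×0.0903 = 0.177.
- Standard error under the alternative = √(0.45×0.55/58 + 0.30×0.70/57) = 0.0892.
- Power ≈ Φ[(0.150 − 0.177)/0.0892] = Φ(−0.30) = 38%.

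Significance therefore needs an observed difference of nearly 18 points, more than the plan's own threshold. Exact enumeration gives 39% for this case, and for a true 15-point gain:

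| Control rate | 5% | 10% | 15% | 20% | 30% | 40% | 50% | 60% | 70% | 80% |
|---|---|---|---|---|---|---|---|---|---|---|
| Gate passed | 71% | 57% | 49% | 44% | 39% | 37% | 38% | 41% | 49% | 73% |

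For a true 20-point gain the gate is passed in 58% to 89% of trials (control 5% to 70%). If 15% is relative, it is passed in only about 6% to 48% (control 20% to 80%).

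**Step 2: what the gate discards.** Simulated trials of 115, 4,000 per row, control rate 30%:
- mediator = a×arm + standard normal noise
- logit(screening) = constant + b×mediator + c×arm

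A trial counts as finding both paths when arm-to-mediator and mediator-to-screening given arm are each significant. Share discarded = (both paths significant, arm effect not) ÷ (both paths significant).

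| a, b, c | Total effect | Arm effect significant | Both paths significant | Both paths, arm effect not | Share discarded |
|---|---|---|---|---|---|
| 0.8, 0.8, 0 | 13 points | 31% | 95% | 66% | 69% |
| 0.6, 0.8, 0.2 | 14 points | 35% | 86% | 54% | 63% |
| 0.6, 0.6, 0.3 | 14 points | 34% | 72% | 46% | 64% |
| 0.8, 0.8, 0.3 | 19–20 points | 59% | 95% | 38% | 40% |
| 0.6, 0.6, 0.6 | 21 points | 65% | 73% | 24% | 33% |
| 0.8, 0.8, 0.5 | 24 points | 76% | 95% | 22% | 24% |

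**Step 3: full mediation at exactly 15 points.** With control rates of 20% to 60% and mediator shifts of 0.5 to 0.8 SD, both paths are significant in 75% to 99% of trials. Adding the gate and the shrinking-coefficient condition leaves 34% to 43%, a loss of 51% to 63%. The gate alone accounts for 46% to 61%. For weaker full mediation (total about 5 to 7 points) the full rule discards 85% to 90%.

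**The case against.** Four points can be made for the plan.

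- **No flat contradiction.** A reader might infer that the two statements cannot both be followed. The opening sentence speaks of each covariate's impact on the outcome, while the rule governs when a covariate is labelled a mediator of the intervention. A team could report every covariate–outcome coefficient and use the label only when the rule is met. This stands. What remains is a conflict with purpose: a covariate–outcome association alone is not mediation, and the sentence is offered as the reason for doing mediation analysis.
- **The loss is conditional.** A reader might infer that the gate would discard most true mediation at this sample size. That is not true in general. At 15 points the gate is passed more often than not when screening without the intervention is rare or very common, and at 19 to 24 points it discards a minority of findings. The 15-point figure is a threshold for calling the intervention effective, not a stated design alternative. These limits stand.
- **No negative report is prescribed.** It is tempting to say that the plan must report an absence of mediators after a null result. The text says only when mediation will be concluded, and the path coefficients would still be available. This stands, but the plan would have no basis for drawing a conclusion from them.
- **The other reading of the rule.** Suppose the indicator must be significant in the model that contains the mediator. A clash with the regression steps is then only partial, because those steps also accept a meaningful reduction in effect. Full mediation, where the arm effect vanishes, would still usually fail. The ambiguity should be removed, but the point does not depend on it.

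**Conclusion.** The point holds in a conditional form. Making a significant arm effect a precondition undercuts the declared aim of the mediation analysis. At a true 15-point absolute gain, it blocks the conclusion more often than not for control rates of about 15% to 70%. For largely mediated effects of 13 to 15 points, the loss among trials with both paths significant runs from about half to about 70%, depending on the assumed paths.

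The blocking probabilities depend on the assumed control rate and on reading 15% as absolute. The discarded shares also depend on the assumed mediator effects. The text conflict depends on none of these. The primary comparison is unaffected; what changes is what the trial can say about why the intervention did or did not work.

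**What to change.** In both mediation passages of the Statistical analysis section:

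1. Remove the significant total effect as a precondition, both in the Baron and Kenny rule and in the regression steps.
2. Remove loss of significance and the shrinking treatment coefficient as criteria. Both still turn on the arm–screening coefficient, so deleting the first condition alone would not be enough. Coefficients from logistic models with and without the mediator are also not directly comparable.
3. State that mediation is analysed whatever the primary test shows. Judge it on the arm-to-mediator path and the mediator-to-screening path given arm, either by joint significance or by an indirect-effect estimate with a bootstrap interval, on a scale suited to a binary outcome.
4. Report the total arm effect alongside.

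The cost is revised wording and a little more analysis; no new data are needed. The section describes the primary comparison in the past tense. If that result is already known, the change must be labelled as made after it.

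### The mediation rule written for the Likert-type items leaves out the arm-to-mediator test that the plan requires for its three named mediators

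*Combined protocol and SAP*

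**What the plan says.** The Statistical analysis section treats mediation in two places.

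- **Named mediators** (perceived susceptibility, self-efficacy, knowledge). The plan will test the arm-outcome relationship, then "the exogenous and mediator variable, the mediator and the endogenous variables in the presence of the IV", and finally "confirm the lack of significance (or the meaningful reduction in effect) of the relationship between X and Y" once the mediators are included. The arm-to-mediator test is therefore explicit. The same part of the section requires every variable to be continuous and normally distributed. On indirect paths it says "We will assess direct causality and indirect causality using standardized regression coefficients".
- **Likert-type items.** A later paragraph covers "each of the short items scored on a Likert-type scale" and states "we will follow the strategy of Baron and Kenny". It then writes its own conclusion rule: "1) the treatment group indicator is significant", the candidate covariate is significant, and "the coefficient estimate of the treatment group indicator is smaller in absolute value than its counterpart in analysis".

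The later paragraph does not refer back to the earlier one, and neither says which governs. It does not identify the counterpart model. No indirect-effect estimate or confidence interval is defined anywhere in the section.

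**The concern.** A mediator must be changed by the intervention and must in turn affect the outcome. The rule for the Likert-type items checks the second link and not the first. In its place it uses the direction of a change in the arm coefficient, with no minimum size and no allowance for sampling error. In a trial of 115 people, chance imbalance in a prognostic covariate will sometimes move the coefficient towards zero, and the rule then reads that imbalance as mechanism.

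The plan says mediation analysis is meant to show why variables are related. A covariate that the programme never moved could be reported as a reason the programme works.

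**Working it through.** **1. The two rules side by side**

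| Step | Named mediators | Likert-type items |
|---|---|---|
| Arm effect on screening significant | required | required |
| Arm effect on mediator significant | required | not listed |
| Mediator effect significant | required, given arm | required |
| Change in arm coefficient | loss of significance or a meaningful reduction (no number) | any decrease |

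**2. Why any decrease is weak evidence.** In a linear model the arm coefficient without the covariate, minus the coefficient with it, equals a × b. Here a is the observed arm difference in the covariate and b is its slope on the outcome. If the true a is zero, the observed a still has the shrinking sign in about half of trials. A logistic model behaves differently: adding a prognostic covariate pushes the arm coefficient away from zero even without mediation. In the simulation below its mean rose from 0.66 to between 0.69 and 0.83 (30% vs 45%), and from 1.28 to between 1.34 and 1.61 (30% vs 60%). This restrains false declarations but does not remove them.

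**3. Inputs.** From the plan: 115 randomized, 1:1 allocation, two-sided 0.05, and a 15% difference as the effectiveness threshold, read here as percentage points. Assumed, because the plan does not give them: screening of 30% vs 45% or 30% vs 60%; a standard normal covariate with odds ratio (OR) 1.5, 2 or 3 per SD; logistic models; the counterpart taken as the arm coefficient without the covariate; condition (1) taken as the unadjusted arm test. There were 20,000 simulated trials per scenario. The plan has no mediation figure to reproduce.

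**4. Check on condition (1).** With 57.5 per arm, power = Φ[(d − 1.96·SE₀)/SE₁].
- 30% vs 45%: SE₀ = √(2 × 0.375 × 0.625/57.5) = 0.0903; SE₁ = √((0.21 + 0.2475)/57.5) = 0.0892; (0.15 − 0.1770)/0.0892 = −0.30, so power is 38% (simulated 39%).
- 30% vs 60%: SE₀ = 0.0928; SE₁ = 0.0885; (0.30 − 0.1819)/0.0885 = 1.34, so power is 91% (simulated 91%).

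**5. Covariate not changed by the programme: trials declaring it a mediator**

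| Screening | OR per SD | Rule as written | With arm-to-mediator test |
|---|---|---|---|
| 30% vs 45% | 1.5 | 6.0% | 0.6% |
| | 2 | 10.2% | 1.6% |
| | 3 | 8.1% | 1.9% |
| 30% vs 60% | 1.5 | 8.5% | 1.1% |
| | 2 | 11.4% | 2.1% |
| | 3 | 5.5% | 1.8% |

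For a five-level Likert item (10,000 trials per scenario) the ranges are 5.4–11.2% and 0.4–2.3%. Allowing for variation between runs, I summarise the two rules as about 5–11% and about 0.6–2.3%.

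The rule can fire only when the arm effect is significant. Among such trials at 30% vs 45%, the rates as written are 6.0/39 = 15%, 10.2/39 = 26% and 8.1/39 = 21%. With the test added they are 0.6/39 = 2%, 1.6/39 = 4% and 1.9/39 = 5%.

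**6. Real mediator, moved 0.5 SD by the programme.** Adding the test changes detection from about 20–38% to about 16–34% at 30% vs 45%, and from about 43–79% to about 34–68% at 30% vs 60%.

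**7. Bootstrap interval.** Without mediation, a bootstrap 95% interval for the indirect risk difference excluded zero in 2.2%, 5.0%, 5.9% and 4.9% of trials (four scenarios, 1,000 trials each, 400 resamples). That is close to nominal or below it.

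**The case against.** The best defence is that the step is already there. The Likert-type paragraph invokes Baron and Kenny by name, and the earlier paragraph spells out the arm-to-mediator test for the only three mediators the plan names. If the short items measure those constructs, the step may be inherited and the gap is one of drafting. This has force and limits the point. It does not remove it, because the later paragraph writes an explicit conclusion rule, and an analyst who follows that rule never tests whether the programme moved the item.

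It is also fair that the sizes rest on assumed rates and odds ratios, and that the plan does not fix the mediation model. Its logistic regression sentence concerns demographic covariates and insurance.

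Three stronger readings are tempting, and the documents do not support them.

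- A reader might infer that the paragraph contradicts itself, since it says impact is assessed "independent of whether the intervention's effect is significant" while condition (1) needs a significant arm effect. That sentence can be read as concerning only each covariate's association with screening, with condition (1) deciding when the covariate is called a mediator of the intervention. Both can hold.
- A reader might infer that coefficient shrinkage in logistic models hides real mediation. In the 0.5 SD scenarios the coefficient shrank in 88–99% of trials that met both significance conditions. Low detection at 30% vs 45% comes from condition (1).
- A reader might infer that Baron and Kenny must be abandoned for a joint test of both paths. That is a choice of method. Without mediation the joint test gives 2.5–5.0% false declarations, more than the written rule with the missing test added (0.6–2.1% in the same runs).

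**Conclusion.** The concern holds as a defect in the written rule for the Likert-type items. That rule omits the arm-to-mediator test required for the named mediators, and nothing ties the two together. Under the stated assumptions the omission raises false declarations from about 0.6–2.3% to about 5–11% of trials per candidate. The gap is narrowest at an odds ratio of 3 with 30% vs 60% (5.5% vs 1.8%). Other rates, covariate strengths or models would change these sizes.

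The reach is limited. Mediation is not among the outcomes listed in the Study Protocol section, and the 12-month screening comparison is untouched. The undefined size of a meaningful reduction and the unstated number of candidates are mainly missing detail. The repair is worth making because it is cheap and protects the claim about why the programme works.

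**What to change.** Add one sentence to the rule for the Likert-type items: the arm effect on the candidate mediator must also be significant, as for the three named mediators. One rule then covers every candidate. In the same edit:

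- identify the counterpart as the arm coefficient from the same model without the candidate;
- specify a logistic model for screening, and drop the continuity and normality requirement for arm and screening, which are both binary and cannot meet it;
- report the indirect effect on the risk-difference scale with a bootstrap 95% confidence interval, instead of relying on any shrinkage of the coefficient;
- label the mediation results exploratory.

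A joint test of both paths is an optional alternative. At 30% vs 45% it would find a 0.5 SD mediator more often (38–76%), because it does not need a significant overall arm effect.

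The cost is a rewording of two paragraphs, a little more analysis and no new data, with the loss of detection shown in step 6 of the working.
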